Surprisingly, none of the prior VLNC treatment studies emphasized strategies that would maximize extinction to cigarette-related reinforcement during the pre-quit period. Theoretically, the sub-threshold nicotine doses with VLNC cigarettes should extinguish both primary and secondary sources of smoking-related reinforcement. The proposed research will develop a behavioral intervention intended to optimize the efficacy of VLNC cigarettes from a learning-based (extinction) perspective. Specifically, the proposed project will (1) develop a theory-driven "facilitated extinction" intervention for use with VLNC cigarettes during the pre-quit period, (2) evaluate the efficacy of pre-quit VLNC cigarette smoking as a cessation strategy by conducting a randomized controlled trial (RCT), and (3) obtain data regarding potential mechanisms that may moderate or mediate treatment effectiveness, to inform future implementation of this novel cessation strategy. If successful, future research may continue to validate this VLNC treatment strategy in comparison with existing methods (e.g., NRT treatment), and determine the most effective methods to disseminate VLNC cigarettes for clinical benefit. Below, we discuss the theoretical foundations of the proposed research.

Facilitated Extinction

Recent advances in learning theory, along with methods from basic and applied research from other domains of psychopathology, can be used to optimize extinction as part of an approach to smoking cessation (e.g., Bouton, 2000; Conklin & Tiffany, 2002; Foa 2011; Laborda et al., 2011). We are currently evaluating such an approach to maximize extinction with extended pre-cessation varenicline. Following strategies employed in that project, we plan to base our initial development of a facilitated extinction workbook for pre-quit VLNC use on the following key techniques:

- a) Ensure that participants continue to smoke VLNC cigarettes at their normal rate during the pre-quit period. This will create maximum opportunities for extinction learning. Thus, premature smoking reduction or cessation will be actively discouraged (in contrast to ongoing smokers who may spontaneously reduce smoking when given VLNC cigarettes).

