3) Practicality represents the broadest of the feasibility constructs. This will encompass the degree to which we are able to carry out all the elements of the planned developmental pilot study successfully and efficiently. This includes recruitment, screening, randomization, and treatment components. For these elements of the study, we will record number of attempts, duration, protocol deviations and errors, and suggestions for improvement.

Study 2. Randomized Controlled Trial (Aim 2), Intermediate Outcomes (Aim 3), and Mechanisms (Aim 4)

Study Goals and Overview. The primary goals of Study 2 are to test effects of the targeted intervention developed in Study 1 on smoking cessation (Aim 2) and intermediate outcomes (Aim 3), as well as to explore potential mechanisms that could guide future implantation of this treatment strategy (Aim 4). Approximately 300 treatment-seeking smokers will be screened using similar methods and inclusion/exclusion criteria as in Study 1. The expectation is that 80% of participants (n=208) will be eligible and randomized to one of four conditions (52 per condition) over a 3 year period. The four conditions will comprise a 2 x 2 between-subjects design, with facilitated extinction (targeted) treatment (present vs. absent) crossed with tapering schedule (immediate vs. gradual). As in Study 1, once a participant has been deemed eligible, a baseline week of smoking NNC study cigarettes will be followed by four weeks of smoking VLNC cigarettes, either through immediate or gradual reduction to the lowest level. Five weekly counseling sessions will occur (at the start of each week), and the Target Quit Date will occur one week after the fifth weekly session (+/- 3 days). On the Target Quit Date, participants will attend an additional session, including counseling as well as two tests of intermediate outcomes (cue reactivity and cigarette purchase task). Follow-up visits will occur at 2 and 6 months following the TQD (+/- 7 days). Please see Appendices on pages 33-34 for further details.

Exclusion Criteria: Study 2 exclusion criteria will match those of Study 1, with the following modifications: (a) use of smoking cessation medications will be exclusionary only for the past month and with the exception of sporadic use of NRT for non-cessation purposes, (b) use of

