Intervention Phase. As in Study 1, all participants will be given a supply of normal nicotine content (NNC; .8 mg yield) study cigarettes to smoke for a baseline week, based on typical # cigarettes/day x 1.5. However, if a participant normally smokes 120mm cigarettes, then the amount supplied will be determined by multiplying their typical number of cigarettes/day x 2 (because the Spectrum cigarettes are regular length at approximately 80mm). This will introduce participants to the taste and feel of Spectrum research cigarettes, prior to receiving reduced nicotine cigarettes, thereby avoiding the confounding of changing brand and nicotine content simultaneously. Prior to the baseline session, participants will be randomly assigned to one of four treatment conditions, that vary according to a 2 x 2 between subject design: (1) targeted intervention with immediate transition to VLNC cigarettes, (2) targeted intervention with gradual transition to VLNC cigarettes, (3) standard intervention with immediate transition to VLNC cigarettes, (4) standard intervention with gradual transition to VLNC cigarettes. Overall, the intervention phase will consist of six visits, with five of them preceding the TQD which will occur one week after the fifth weekly session. The sixth session will occur on the TQD. At each of the pre-quit visits, participants will (1) receive their supply of study cigarettes for the upcoming week, (2) complete assessments related to compliance and reactions to assigned study cigarettes, (3) answer questions regarding health changes (if any) and date/length of last menstrual period for pre-menopausal women (to assess potential pregnancy), which will be documented on the 'Health Changes Questionnaire' (4) complete a Cigarette Purchase Task for their study and usual brand cigarettes (5) complete the QSU-brief for study and usual brand cigarettes (6) complete a Cigarette Evaluation Scale for the study cigarettes (7) complete the Drug Effects/Liking Scale for their study cigarettes (8) complete the Timeline-Follow Back interview to update their smoking, alcohol, and drug use since the prior visit, and (9) receive brief counseling according to condition. As in Study 1, if the participant's breath alcohol level is > 0.03 the researcher will not start the session.

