Aim 2 – Treatment Efficacy. Analyses will focus on the incremental efficacy of targeted intervention, in combination with two tapering regimens for transition to VLNC cigarettes during the pre-quit period, on clinical outcomes. The primary outcome variable will be 7-day point prevalence abstinence at each follow-up assessment, with secondary outcomes that include continuous abstinence since the TQD, days to first smoking lapse, and smoking reduction relative to baseline (see Ditre et al., 2012). Mixed modeling will be used to test hypotheses related to these treatment outcome effects. The advantages of these models is that they allow for data that is missing at random and are more flexible than repeated measures ANOVA in terms of the underlying variance/covariance matrix (Littell et al., 2006). For point prevalence and continuous abstinence variables, a 2 (intervention: targeted vs. standard) x 2 (transition: immediate vs. gradual) analysis will be used to test the independent and combined effects of each treatment factor on these cessation outcomes, using Generalized Estimating Equations (GEE) with a logistic function for dichotomous outcomes.

Aim 3 - Intermediate Outcomes. Aim 3 includes testing effects of the intervention on intermediate (proximal) outcomes during the cue reactivity and cigarette purchase tasks. Findings may support decisions regarding which tapering schedule is optimal for further testing and/or dissemination, and may provide insight as to the mechanisms that underlie positive cessation outcomes. As in Aim 2, mixed modeling will be used to independently test the effects of targeted intervention and tapering schedule on outcomes from these two paradigms. Indices of smoking-related behavior from each paradigm (cue reactivity: self-reported craving in response to smoking cues; cigarette purchase task: hypothetical cigarette consumption across a range of prices) will be examined through separate models that test effects of intervention (targeted vs. standard) and tapering schedule (immediate vs. gradual) on these outcomes. In addition, Generalized Estimating Equations (GEE) models with a logistic function will be used to examine intervention effects on dichotomous outcomes.

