- Cardiovascular disease (CVD) event: typically includes MI (heart attack), PTCA (angioplasty/stenting), bypass surgery, stroke, peripheral vascular disease (arterial blockages in arms or legs leading to procedure or surgery). Less common CVD problems would be new cardiac arrhythmias (e.g., new atrial fibrillation) or new valvular disease (e.g., mitral or aortic regurgitation.)
- 2. DVT/PE (deep vein thrombosis/pulmonary embolism, i.e., blood clots in the venous system)
- 3. Suicide Attempt: A participant will be withdrawn if he/she attempts suicide at any time during participation in the study.
- 4. Psychiatric Hospitalization: A participant will be withdrawn if he/she is hospitalized for psychiatric reasons at any time during participation in the study.
- 5. Pregnancy: If a participant indicates she is pregnant or has a positive pregnancy test, she will be withdrawn from the study. Approximately 30 days after being withdrawn, the research staff will contact the participant to confirm her due date. This event will remain open until delivery. At that time the study physician (or licensed medical professional designated to consult in his absence) will contact the participant to ask a few questions about the baby's health and will update the open 'Adverse Event Form'.
- 6. Expired breath CO increase: A participant will be withdrawn from the study if the average of two consecutive CO readings during the same visit is 100 ppm or greater.

Withdrawal Rules: In order to detect significant increases in smoking due to study cigarettes (e.g., compensatory smoking), which could signal increased cardiovascular risk, we will apply guidelines for discontinuation of VLNC smoking due to marked increases in carbon monoxide (CO) levels or smoking, as follows:

- a) If the average of two consecutive CO readings during the same visit is 100 ppm or greater
- b) If both of the following criteria are met for two consecutive weeks:
 - 1. Cigarettes per day (CPD) increase: The average CPD increases by more than 100% from the average CPD during baseline
 - 2. Expired breath CO increase; If the average of two consecutive CO measurements in the same visit is:
 - i. CO is greater than 50 ppm if CO at baseline is < 20 ppm
 - ii. CO is greater than 60 ppm if CO at baseline is 20 34 ppm
 - iii. CO is greater than 70 ppm if CO at baseline is 35 49 ppm
 - iv. CO is greater than 80 ppm if CO at baseline is 50 64 ppm
 - v. CO is greater than 90 ppm if CO at baseline is 65 80 ppm

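### The baseline for the smoking-reduction outcome is not defined, and one of its two candidates, the normal-nicotine study-cigarette week, follows randomisation and condition-specific counselling

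*Combined protocol and SAP*

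**What the plan says.** Statistical Considerations, Aim 2 – Treatment Efficacy, makes 7-day point prevalence abstinence the primary outcome. It names as secondary outcomes "continuous abstinence since the TQD, days to first smoking lapse, and smoking reduction relative to baseline". No reference period is given for the last of these.

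Elsewhere the word baseline has two uses in Study 2:

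- **Visit 1.** The Baseline/Screening Session includes the Smoking Timeline Follow-Back interview. The Appendix table of procedures lists it at Visit 1 as a 30-day version.
- **The week after Visit 1.** Study Goals and Overview states that "a baseline week of smoking NNC study cigarettes will be followed by four weeks of smoking VLNC cigarettes". The Intervention Phase section says "all participants will be given a supply of normal nicotine content (NNC; .8 mg yield) study cigarettes to smoke for a baseline week".

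On timing, the Intervention Phase section states: "Prior to the baseline session, participants will be randomly assigned to one of four treatment conditions". Study Goals and Overview states: "Five weekly counseling sessions will occur (at the start of each week"). The list of what happens at each pre-quit visit ends "and (9) receive brief counseling according to condition".

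The withdrawal criteria also rely on baseline cigarettes per day (CPD). The Withdrawal Rules say "The average CPD increases by more than 100% from the average CPD during baseline". The list that follows, of events that can lead to withdrawal, compares average CPD with its value at baseline. Neither place defines the period.

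**The concern.** A reference value for change should be fixed before treatment can alter it. The NNC week does not meet that test for the intervention factor: participants have already been assigned and have had one session of counselling that differs between the targeted and standard arms.

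The plan itself treats smoking rate before the quit date as something the intervention may move. In the Facilitated Extinction section of the Significance chapter, the targeted approach asks for smoking at the normal rate, and "premature smoking reduction or cessation will be actively discouraged". Aim 4 lists compliance with the pre-quit VLNC smoking rate as a potential mediator.

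With the baseline undefined, an analyst could choose either candidate, possibly after seeing data. Under one of them, a difference between arms in the NNC week would appear as a difference in smoking reduction even if smoking at follow-up were identical.

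**Working it through.** **1. Order of events in Study 2**

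| Step | Source |
|---|---|
| Assignment to one of four conditions, before Visit 1 | Intervention Phase |
| Visit 1: 30-day Timeline Follow-Back, covering days before any study counselling | Smoking-related measures; Appendix table |
| Visit 1: first counselling session, and supply of NNC cigarettes | Study Goals and Overview; Intervention Phase; Appendix table (counselling notes marked at Visit 1); COVID-19 modifications (counselling at the screening visit) |
| NNC week | Study Goals and Overview |
| Visit 2: smoking in that week first recorded | Appendix table |

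There are five study-cigarette weeks (1 NNC + 4 VLNC) and five counselling sessions, one opening each week. Session 1 therefore opens the NNC week. The Timeline Follow-Back describes a period before counselling; the NNC week does not.

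**2. The plan's own figure**

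The plan gives no figure for smoking reduction. Its power statement concerns abstinence: 20% in the standard arm, about 18 points more in the targeted arm, 104 per arm, two-sided alpha .05. With mean proportion 0.29:

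- Null SE = √(2 × 0.29 × 0.71 / 104) = 0.0629; alternative SE = √((0.20 × 0.80 + 0.38 × 0.62) / 104) = 0.0617.
- Power = Φ[(0.18 − 1.96 × 0.0629) / 0.0617] = 0.82. Fisher's exact test gives 0.78.

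The stated 0.80 reproduces. Baseline CPD does not enter it, so the choice of baseline leaves it unchanged.

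**3. What the NNC week could do as a reference**

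None of the inputs here is in the documents; all are assumptions. Let pre-study smoking B and follow-up smoking F be the same in both arms, so that there is no true effect. Let the targeted arm smoke B in the NNC week and the standard arm B(1 − s).

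- Spurious difference in absolute reduction (targeted minus standard) = (B − F) − (B(1 − s) − F) = B·s.
- Spurious difference in percent reduction = (F/B) × s/(1 − s).

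With B = 15 and F = 7.5:

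| s | CPD | Percentage points |
|---|---|---|
| −5% | −0.75 | 0.5 × (−0.05/1.05) = −2.4 |
| 0 | 0 | 0 |
| 5% | 0.75 | 0.5 × 0.05/0.95 = 2.6 |
| 10% | 1.5 | 0.5 × 0.10/0.90 = 5.6 |
| 20% | 3.0 | 0.5 × 0.20/0.80 = 12.5 |

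A negative s, meaning the standard arm smokes more that week, reverses the sign. The documents do not determine s.

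To see what such a shift does to a test, assume also an SD of 8 CPD for change. With 104 per arm, SE = 8 × √(2/104) = 1.11. Two-sided type I error is then 0.10 at a shift of 0.75 CPD and 0.27 at 1.5 CPD. With 69 per arm (half of the 138 expected at 6 months), it is 0.085 and 0.20.

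**4. Using the NNC week as a covariate**

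If follow-up CPD is regressed on arm and NNC-week CPD with slope b, the same assumptions give a spurious difference of b·B·s. For b between 0 and 1 this shrinks the problem but does not remove it.

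**5. The Visit 1 reference**

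The 30-day period precedes study counselling and study cigarettes, so randomisation makes the expected arm difference zero and this bias disappears. It is also more complete: the Project Timeline note expects 208 baseline sessions and 198 at pre-quit week 1, so NNC-week smoking would be missing for about 208 − 198 = 10 participants.

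**The case against.** A reader might infer that smoking reduction is already measured against the NNC week and is therefore biased. The documents do not support that. The Aim 2 text never names the week, and most uses of baseline elsewhere mean Visit 1. On that reading the reference is already the Timeline Follow-Back and there is no bias.

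A reader might also infer that counselling pushes smoking in opposite directions during that week. This is not documented either. The instruction to keep to the normal rate is worded for VLNC cigarettes in the pre-quit period. The Study 1 Intervention Phase section and the Project Timeline note list the baseline week apart from the four pre-quit weeks, although Study 2 counts five visits before the quit date. The standard arm receives cognitive-behavioural cessation counselling of equal duration, and nothing tells it to cut down before the quit date. First-session content is not given. The generous cigarette supply applies to every arm.

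Finally, the plan cites a published study beside its list of secondary outcomes, which might define the measure. That cannot be checked here, and the plan should carry its own definition.

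These points stand, and they limit the concern to an ambiguity with a risk attached. They do not remove it: the sequence is documented, both candidates bear the same name, and only one is free of possible treatment influence.

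**Conclusion.** The concern holds in a limited form. The reference for one secondary outcome is undefined, and one of the two periods called baseline follows randomisation and a first condition-specific session. If that week were used as reference or covariate, the targeted-versus-standard comparison on smoking reduction could be biased. Direction and size cannot be derived from the documents, and zero is possible. The illustrative 0 to 3.0 CPD rests on assumed values of usual smoking and of the arm difference in that week; the type I error figures also rest on an assumed SD.

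The primary abstinence outcome, its power, continuous abstinence and days to first lapse do not use this reference. Nor is the tapering comparison affected: all participants smoke the same NNC cigarettes that week, and counselling differs only by intervention.

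In the withdrawal criteria, baseline CPD is undefined in both places. The difference in phrasing does not by itself show that two different periods are meant.

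**What to change.** In Aim 2 – Treatment Efficacy:

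- Define baseline for smoking reduction as mean cigarettes per day from the Visit 1 30-day Timeline Follow-Back, and state that it is completed before any study counselling or study cigarettes.
- Analyse follow-up cigarettes per day in the planned mixed model, adjusted for that value.
- State that NNC-week smoking will be neither the reference nor a covariate in this analysis.

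Adjusting for the pre-treatment value is also generally more precise than a change score. With equal variances and correlation ρ between baseline and follow-up, the variance ratio is (1 − ρ²) / (2(1 − ρ)) = (1 + ρ)/2, which is below 1 for any ρ below 1.

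The cost is wording only, since the interview is already scheduled at Visit 1. The downside is that the reference is recalled usual-brand smoking rather than a week on study cigarettes.

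Separately, the sponsor should reconcile the Withdrawal Rules and the monitoring list that follows them, so that each says which period baseline CPD refers to. No withdrawal rule is proposed here.

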Sample Size Determination. The planned sample size (n=20) for the developmental pilot study (Study 1; Aim 1) is based on considerations of practicality and usefulness. A primary focus of Study 1 will be on evaluation of feasibility (acceptability, demand, practicality) of the procedures, and determining potential improvements to incorporate into the subsequent RCT (Study 2). In the context of the goals and project timeline, the planned sample size for the developmental pilot study should provide the team with ample information to inform the RCT (Study 2). The planned sample size (n=208) for the RCT (Study 2) is based on considerations of statistical power and anticipated effects for the primary hypothesis regarding treatment outcomes (Aim 2). We assume those who receive the standard intervention (n=104) will achieve a 20% 7-day point prevalence abstinence rate at the 6-month follow-up. Based on an intent-totreat data analytic approach and a two-sided alpha = .05, the proposed sample will have .80 power to detect approximately an 18% improvement in abstinence rate among those who receive the targeted intervention. This magnitude of improvement would be clinically significant. and worthy of further refinement and application. A similar magnitude of effect would be detectable as a function of tapering schedule. No interaction effects (between intervention and tapering schedule) are predicted. Power is likely to be greater for detecting treatment effects on dichotomous cessation outcomes at the 2-month follow-up, continuous cessation outcomes at both follow-up timepoints, and intermediate (proximal) behavioral outcomes (Aim 3). Moreover, within-condition correlations as small as 0.28, and total-sample incremental R^2 as low as 0.07 (based on six predictors) would be detected, suggesting that the moderator analyses (Aim 4) would be adequately powered to detect clinically significant effects.

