Aim 1 - Feasibility. The developmental pilot study will obtain data that will help determine the feasibility of the targeted treatment materials and the methodology for examining its efficacy in Study 2. We conceptualize feasibility as a multidimensional construct, as suggested by the multiple indices (described above) that we will collect. Each feasibility index will either be compared to published norms (e.g., for the CSQ) or our prior experience with clinical trials for smoking cessation, or subject to evaluation by the investigative team (including consultants). We expect that we will be able to recruit adequate numbers of eligible participants during the study timeframe with efficient cost expenditures, retain 80% through the end of the treatment phase, and retain 70% through the end of the follow-up phase. Furthermore, indices of treatment acceptance and satisfaction for those who receive the targeted intervention are expected to be 80% or higher. Finally, participants are expected to comply with use of VLNC cigarettes (e.g., >80% exclusive use of VLNC cigarettes). For any indices that fall below expectations, the research team will judge the impact of its underperformance upon the planned RCT (Study 2) and/or treatment dissemination and implementation, and whether corrective actions are possible. The team will take performance across all indices into account when determining whether modifications are warranted prior to the planned RCT.

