intervention development and testing, we hope to reduce participant burden and expense, and more closely represent a real-world application of this potential treatment method. Nonetheless, we will carefully track smoking rate (all sessions), carbon monoxide (all sessions), and urinary cotinine (baseline and follow-up sessions, as applicable) levels, and use medically established cut-offs (established by the Center for the Evaluation of Nicotine in Cigarettes; U54, MPI's: [name]/[name]) to guide decisions regarding early termination.

Project Timeline

Study 1 is expected to comprise the first 1.5 years of funding (see details above). Study 2 will be completed over the remaining 3.5 years (Table 2).

| Task | | Year 1 | | Year 2 | | Year 3 | | Year 4 | | ar 5 |
|---------------------------------|---|--------|---|--------|---|--------|---|--------|---|------|
| Study 1 | X | X | X | | | | | | | |
| Study 2 - Recruitment | | | | X | X | X | X | X | X | |
| Study 2 - Follow-up Assessments | | | | | X | X | X | X | X | X |

Table 2. Project Timeline

Note: Expected number of sessions for Study 2 is 208 screening/baseline, 198 week 1 pre-quit, 188 week 2 pre-quit, 178 week 3 pre-quit, 168 week 4 pre-quit, 158 target quit date, 148 2-month follow-up and 138 6-month follow-up which equals 1384 sessions in 42 months. This is approximately 33 sessions/month.

Participant Compensation (cash or gift card):

- Participants will receive \$25 for completing the baseline session. If an additional visit is needed (e.g., to rescreen for alcohol or drugs, or due to a pending LMP/PI/Co-I eligibility determination), a \$20 payment will be provided for completing the additional visit.
- Following the screening visit, they will receive \$25 for completing each weekly session (including Target Quit Date for Study 2), and an additional \$10 for each session in which they arrive on time, without rescheduling, and bring the treatment booklet with tracking exercises completed.
- COVID-19 considerations: The \$10 weekly session bonus will apply to timeliness and preparedness regarding the in-person assessments, as well as the timely completion of telephone assessments.
- -
- For Study 1 they will receive \$35 for completing a follow-up session after the TQD. This session will include brief counseling, as well as obtaining feedback using a standardized form and a debriefing interview.

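### Days to first smoking lapse, a right-censored secondary outcome, has only a general mixed-modelling statement: no time-to-event method and no rule for participants without an observed lapse day

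*Combined protocol and SAP*

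**What the plan says.** Under Statistical Considerations, Aim 2 – Treatment Efficacy, the primary outcome is 7-day point prevalence abstinence at each follow-up. The secondary outcomes are "continuous abstinence since the TQD, days to first smoking lapse, and smoking reduction relative to baseline". The next sentence covers the whole list: "Mixed modeling will be used to test hypotheses related to these treatment outcome effects". The reason given is general: "The advantages of these models is that they allow for data that is missing at random", together with more flexibility than repeated measures ANOVA. A more specific method follows, opening "For point prevalence and continuous abstinence variables": a 2 x 2 logistic GEE. Days to lapse is not in that sentence.

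The supplied text names no time-to-event method and does not mention censoring. Sample Size Determination states an intent-to-treat approach for the abstinence endpoint but does not apply it to this outcome. Aim 4 repeats the Aim 2 models with moderator interactions, so the gap carries over to any moderator analysis of days to lapse.

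Under Smoking Cessation Outcomes, lapse information comes from self-report on each of the first seven days and from the Timeline Follow-Back at 2 and 6 months.

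**The concern.** Each participant contributes a single lapse time. With no repeated measure, a mixed model adds nothing to an ordinary comparison of mean days.

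Some participants have no lapse day at all. Someone abstinent throughout is known only to exceed the follow-up period. That value is absent because it is large, which is not what the missing-at-random remark describes. Someone lost while abstinent is known only to exceed the last contact. To fit the stated model the analyst must invent a value or leave a blank, and the plan does not say which. The result then depends on a coding choice that could be made after the data are seen.

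**Working it through.** **The plan's own figure.** The only Aim 2 power statement concerns point prevalence: "We assume those who receive the standard intervention (n=104) will achieve a 20% 7-day point prevalence abstinence rate at the 6-month follow-up", with 0.80 power for an improvement of about 18 points. Pooled two-sided test, n = 104 per intervention level, 20% vs 38%, mean rate 0.29:

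- Power = Φ[(0.18·√104 − 1.96·√(2·0.29·0.71)) / √(0.20·0.80 + 0.38·0.62)]
- = Φ[(1.836 − 1.258)/0.629] = Φ(0.919) = 0.82

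At exactly 0.80 power the detectable difference is 17.5 points (18.6 with continuity correction). The stated figure is reproduced. It says nothing about days to lapse, for which no power is stated.

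**Inputs for days to lapse.**

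- Attrition, from the Table 2 note under Project Timeline: "158 target quit date, 148 2-month follow-up and 138 6-month follow-up". That is 158/2 = 79 per intervention level at the target quit date (TQD), and (158 − 138)/158 = 12.7% lost afterwards. These are session counts; telephone and mail follow-up may make true loss smaller.
- Lapse-free rates at 180 days (assumed): 20% vs 38%, 10% vs 22%, 5% vs 12%. The first pair uses the planned point-prevalence rates, probably an upper bound because a person abstinent at 6 months may have lapsed earlier.
- Curves (assumed): Weibull with a common shape of 0.3, 0.5, 0.7 or 1.0, hence proportional hazards; independent exponential loss.

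**Simulated power**, 4,000 trials per scenario, Monte Carlo standard error about 0.007, 12.7% loss. The ranges span the four shapes.

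| Lapse-free rates | Times censored | Log-rank | Last contact scored as lapse day, t-test | Power lost |
|---|---|---|---|---|
| 20% vs 38% | 30–33% | 0.75–0.77 | 0.65–0.72 | 5–10 points |
| 10% vs 22% | 17–20% | 0.66–0.67 | 0.59–0.63 | 4–7 points |
| 5% vs 12% | 10–12% | 0.52–0.54 | 0.48–0.52 | 3–6 points |

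Against the true difference in mean days to lapse truncated at 180, last-contact scoring is 6–8% too small. With no loss the power cost is 2–6 points and there is no shrinkage.

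**Hand check of the log-rank column.** Under proportional hazards HR = ln S₁ / ln S₀, events D = 158 × (1 − censored share), and power = Φ(√(D/4)·|ln HR| − 1.96).

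- 20% vs 38%: HR = 0.968/1.609 = 0.60; D = 106 to 111; power 0.74–0.76.
- 10% vs 22%: HR = 1.514/2.303 = 0.66; D = 126 to 131; power 0.65–0.67.
- 5% vs 12%: HR = 2.120/2.996 = 0.71; D = 139 to 142; power 0.53–0.54.

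These agree with the simulation.

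**If non-lapsers were left missing.** A t-test on observed lapses only has power of about 0.13–0.25 across the three rate pairs, because the treatment successes are removed.

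**Type I error.** With no effect (20% vs 20%) and equal 12.7% loss, the rejection rate is 0.044–0.054 for every method.

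**The case against.** **The wording is loose.** The Aim 2 paragraph places GEE under the same mixed-modelling statement, so the phrase may be an umbrella and not a commitment to a linear model for lapse days. This stands in part: it is safer to say that the method is unspecified beyond a general statement. The gap remains, because no other method or censoring rule appears. A study cited beside the outcome list may define the outcome, but the plan does not say that its methods are adopted.

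**A reader might infer that the plan discards abstainers.** No text prescribes leaving non-lapsers missing. The low power for that coding also rests on proportional hazards. With an assumed early effect that fades (lapse-free 50% vs 72% at day 7, 20% vs 25% at day 180), the lapsers-only test rejected more often than log-rank (0.67 vs 0.50). It is still invalid, since it conditions on an event after randomisation, but the 0.13–0.25 is not general. Log-rank still beat last-contact scoring by 2–7 points in all four non-proportional shapes tried.

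**A reader might infer a false-positive problem.** With an assumed 8% vs 18% loss and no effect, last-contact scoring rejected in 0.053–0.064 of trials. The documents give no loss by arm, and the excess is small.

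**A reader might take the expectation to "retain 80% through the end of the treatment phase, and retain 70% through the end of the follow-up phase" as RCT retention.** It stands in the Aim 1 feasibility paragraph about the pilot, which omits extended follow-up, so it is not used here.

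**The consequence is modest.** This is one of several secondary outcomes, with no power claim attached. That is correct.

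**Conclusion.** The point holds as an incomplete specification of one secondary outcome. A mixed model is not suited to a single right-censored time, and the plan has no rule for participants without an observed lapse day. Under the assumed curves and the plan's session counts, the plausible cost is about 3–10 points of power and a difference understated by about 6–8%. Smaller loss gives smaller figures. Leaving non-lapsers missing would be far worse, but it is a possible reading that the plan does not direct.

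A reader might also infer that the trial's main conclusion is at risk. The documents do not support that: the primary outcome has its own GEE, and the sample size was set on point prevalence and reproduces. Besides days to lapse itself, only moderator analyses of it under Aim 4 are touched. The change should be made, but the trial does not depend on it.

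**What to change.** For this outcome, replace mixed modelling with Kaplan-Meier curves and a log-rank test or a Cox model with intervention and tapering as factors. Measure time from the TQD. Censor participants who have not lapsed at the 6-month assessment.

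Pre-state one rule, consistent with the intent-to-treat approach in Sample Size Determination, for participants lost while abstinent and for those with no data after the TQD: either censored or counted as lapse. Use the other convention as a sensitivity analysis and report the numbers by arm.

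Confirm that the Timeline Follow-Back at 2 and 6 months covers the whole period since the previous assessment. The plan gives a 30-day version at screening and a since-last-visit window before the TQD, but no window for these two visits. Where coverage is incomplete, or for mail-only responders, for whom only the follow-up questionnaire is described, treat the lapse day as interval-censored or state a dating rule.

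The cost is analysis-plan wording and one sensitivity analysis. Neither convention is free. Censoring at day 0 removes about 104 − 79 = 25 of 104 per intervention level (24%) from the comparison. Counting those 25 as day-0 lapses lowers log-rank power to 0.63–0.65 (20% vs 38%) or 0.55–0.57 (10% vs 22%), and to 0.59–0.62 or 0.52–0.55 if later loss also counts as lapse. Day-0 coding can remove the gain over last-contact scoring: at 5% vs 12% log-rank is then 0–2 points lower.
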